3.0 Inclusion and Exclusion Criteria

We propose a multi-site randomized controlled trial of inpatient integrated palliative and transplant care versus transplant care alone in 360 patients with hematologic malignancies hospitalized for HCT and 180-360 of their caregivers. Patients will be recruited from the MGH Cancer Center, Fred Hutchinson Cancer Research Center, and Duke University. Patients will be randomized in 1:1 fashion and stratified by study site and transplant type (autologous vs. allogeneic). As autologous and allogeneic HCT have significantly different courses of recovery post-transplant,¹ we will stratify by the type of transplant to ensure adequate and balanced representation between the two study groups.

3.1 Screening Procedures:

All participating sites have an admission database which includes all planned HCT admissions. The site PIs will grant the research assistant (RA) at that site access to the database to review the weekly list of scheduled admissions for transplant to screen for eligible patients. Transplant admissions are always scheduled in advance, thus our screening method will ensure we identify all patients who are eligible for

PROTOCOL TITLE: Multi-Site Randomized Trial of Inpatient Palliative Care for Patients with Hematologic Malignancies Undergoing Hematopoietic Stem Cell Transplantation

study participation. We utilized these study procedures in our prior single center trial and enrolled 86% of potentially eligible participants.

3.2 Eligibility Criteria

Patient Inclusion Criteria

- 1) adult patients (≥ 18 years) with hematologic malignancy admitted for autologous or allogeneic HCT.
- 2) ability to read and respond to questions in English or Spanish or to complete questionnaires with assistance from an interpreter.

Patient Exclusion Criteria

- 1) Patients undergoing HCT for benign hematologic conditions
- 2) Patients undergoing outpatient HCT.
- 3) Patients with psychiatric or cognitive conditions which the treating clinicians believes prohibits compliance with study procedures.
- 4) Patients who already consulted Palliative Care during their HCT admission

Caregiver Eligibility Criteria:

- 1) adult (≥ 18 years) relative or a friend of a patient who agrees to participate in the study whom the patient identified as living with them or having in-person contact with him or her at least twice per week.
- 2) ability to read and respond to questions in English or Spanish or to complete questionnaires with the assistance of an interpreter.

Given the different needs of children with hematologic malignancy undergoing HCT, we will enroll patients at least 18 years of age, in approximately equal numbers of men and women who represent the cultural and demographic backgrounds of the patients seen at our participating sites. We will not include pregnant women or prisoners in this study.

4.0 Study-Wide Number of Subjects

We propose a multi-site randomized controlled trial of inpatient integrated palliative and transplant care versus transplant care alone in 360 patients with hematologic malignancies hospitalized for HCT and 180-360 of their caregivers.

5.0 Study-Wide Recruitment Methods*

5.1 Recruitment and Enrollment Procedures:

We will use the same successful recruitment and enrollment procedures from our prior single center trial. Prior to the study start, the site investigators will meet with the transplant oncology team to review recruitment and enrollment procedures. Specifically, the RA will send an email to the transplant clinicians to notify them that their patient (and caregiver) is eligible for study participation and inquire about any concerns regarding their participation [appendix J]. If the clinicians have objections to their patients' and/or caregivers' participating in the study, the RA will document the reason and not approach those individuals. If the transplant clinicians have no objections, the RA will approach patients for study participation two weeks prior to their admission date or within 72 hours of their admission for HCT (excluding public holidays, in which case the RA will approach within 96 hours). The RA will conduct informed consent procedures with potential participants and obtain written informed consent or verbal

PROTOCOL TITLE: Multi-Site Randomized Trial of Inpatient Palliative Care for Patients with Hematologic Malignancies Undergoing Hematopoietic Stem Cell Transplantation

consent over the telephone or a video call. Patients being contacted for verbal consent will be contacted twice a week during the two weeks prior to their transplant admission. If we are unable to contact the patient, we will leave a voicemail with our study contact information. Patients providing verbal consent will be sent an unsigned copy of the informed consent form for their records. Patients will then be asked to identify a caregiver who might be interested in participating. Patients without a willing or interested caregiver will still be eligible to participate in the study. The caregiver will be eligible to enroll in the study either at the same time as the patient or within 72 hours after the patient provides verbal or written informed consent. We will have a separate consent form for caregivers, which will similarly detail the study procedures. Caregivers will have the option of enrolling in the study in-person with a written informed consent or over the telephone with a verbal consent (Appendix N). Patients and/or caregivers who refuse study participation will be asked the reason for deferring. Study participants will complete baseline self-report assessments on the same day as providing verbal or written informed consent or within the two-week window prior to their admission date or within the 72-hour window (excluding public holidays) from admission to the transplant unit.

Patients and caregivers who speak Spanish will have all study procedures and information regarding risks, benefits and study contacts explained to them orally via the use of an interpreter as a first preference, or family member as a second preference. Spanish speaking participants will be given the DF/HCC Spanish consent short form for signing, as well as a copy of the full English consent form for their own reference. Both the Spanish consent short form, and the full English consent form will be signed by the participant, and by a witness. The witness will be either an interpreter or a family member.

***We are requesting a Waiver of Written Documentation of Consent**

This Waiver is being requested to assist with patient recruitment during the COVID-19 pandemic. Our study meets the waiver requirements given our study is considered minimal risk and all study procedures could be conveyed orally. This waiver will reduce the risk to patients and is necessary for our research procedures to continue.

***We are requesting an HIPAA Waiver of Authorization to Review Preparatory to Research from the IRB.** This Waiver is being requested to identify potential participants from a minimal chart review. In accordance with the DF/HCC policy, this Waiver: (1) is being sought solely to review Protected Health Information as necessary to prepare a research protocol, (2) will not include removing Protected Health Information from the Covered Entity by the researcher, and (3) the Protected Health Information for which we are requesting access is necessary for the research purposes.

Patients will complete baseline self-report assessments at the time of obtaining informed consent for the study or within the two-week window prior to their admission date or within the 72-hour window (excluding public holidays) from admission to the transplant unit. Patients must sign informed consent or provide verbal consent and complete the baseline questionnaire before registering with the Clinical Trials Management System. If patients consent, but do not complete baseline questionnaire, they will not count towards accrual numbers. Caregivers will have 72-hours from patient enrollment to enroll in the study and complete baseline self-reported measures. If caregivers sign the consent, but do not complete baseline questionnaire, they will not count towards the caregiver accrual numbers. Participants who withdraw from the study or die during the study period will not be replaced and they will count towards the accrual numbers.

DF/HCC institutions will register eligible participants in the Clinical Trials Management System (CTMS) Oncore as required by DF/HCC SOP REGIST-101. Registration must occur prior to the initiation of protocol-specific procedures or assessments.

PROTOCOL TITLE: Multi-Site Randomized Trial of Inpatient Palliative Care for Patients with Hematologic Malignancies Undergoing Hematopoietic Stem Cell Transplantation

For registration of patients from DF/HCC institutions, study staff will complete the DF/HCC protocol-specific eligibility checklist using the eligibility assessment documented in the participant's medical record and/or research chart. Study staff will confirm that the participant meets all inclusion criteria as described in this protocol and the criteria on the eligibility checklist.

Patients from other investigative sites will be entered on the study centrally by MGH study staff. Study staff from the participating institution will confirm eligibility criteria and fax or email the following documents to study staff at MGH: deidentified signed consent form/s, and a completed eligibility checklist. MGH study staff will follow DF/HCC Standard Operating Procedure for Human Subject Research Titled *Subject Protocol Registration* (SOP #: REGIST-101) and register the participant on the protocol. Once the patient has been registered, a member from of the MGH Cancer Outcomes Research Program (CORE) team (independent from the study staff) will perform randomization procedures using a computer-generated randomization schema, stratified by study site and transplant type. MGH study staff will fax or e-mail the information about randomization to the study staff at the participating site. MGH study staff may also call the research nurse or data manager at the participating site to verbally confirm registration and randomization.

5.2 Site Investigators and Study Staff Training:

We will conduct an in-person centralized training at MGH for the site lead investigators (site PIs) and RAs to ensure consistent recruitment and enrollment procedures across study sites. We will train the investigative team on: 1) identifying potentially eligible patients via the admission database; 2) tracking potentially eligible patients until their admission for HCT; 3) communicating with oncology clinicians about patient eligibility; 4) obtaining written informed consent from patients and caregivers; and 5) monitoring patients and caregivers longitudinally and administering study questionnaires. Additionally, the site lead investigators will attend the palliative care training described below in-person during their MGH visit.

5.3 Palliative Care Clinician Training

Given heterogeneity in palliative care practices, all participating palliative care clinicians will undergo training and ongoing supervision to ensure that the provision of palliative care services is consistent across study sites. Our research team developed the palliative care intervention guide based on our prior study describing the longitudinal physical and psychological symptom burden in patients undergoing HCT and their caregivers. We refined the intervention guide after conducting qualitative interviews with the palliative care clinicians who participated in our single-site trial. The intervention guide does not manualize the timing of addressing each of the content areas or specific symptoms, as the relevance of the topics (e.g., management of specific symptoms, patient coping, or management of expectations) is dependent on each patient's course during his or her HCT hospitalization. However, it does provide guidance for palliative care clinicians about addressing each content area, when appropriate during the patients' transplant course. We have utilized palliative care intervention guides in our prior multi-site studies to ensure intervention fidelity. Prior to the study start, all participating palliative care clinicians will attend a full-day training using video conferencing to review the intervention guide (the site lead investigators will complete this during their in-person training at MGH). Drs. [name] and [name] will lead these sessions at MGH. Drs. [name] and [name] will also lead monthly supervision calls with the participating palliative care clinicians throughout the trial conduct.

6.0 Multi-Site Research*

PROTOCOL TITLE: Multi-Site Randomized Trial of Inpatient Palliative Care for Patients with Hematologic Malignancies Undergoing Hematopoietic Stem Cell Transplantation

6.1 Communication across sites

[name] and the MGH study team will be responsible for managing communication with all participating sites. [name] will conduct a monthly phone call with the site-Principal Investigators to ensure adequate oversight on the following:

- Understand and communicate the policies and processes of IRB, and be familiar with the research.
- Assist participating sites in obtaining local IRB approval for the protocol.
- Ensure that all participation sites will have the most current version of the protocol, consent document, and HIPAA authorization.
- Ensure that all required approvals (initial, continuing review and modifications) have been obtained at each site (including approval by the site's IRB of record).
- Ensure that all modifications have been communicated to sites, and approved (including approval by the site's IRB of record) before the modification is implemented.
- All engaged participating sites will safeguard data, including secure transmission of data, as required by local information security policies.
 - All local site investigators conduct the study in accordance with applicable federal regulations and local laws.
- All non-compliance with the study protocol or applicable requirements will be reported in accordance with local policy.

6.2 Methods of communication with participating sites:

[name] will lead a monthly meeting with participating sites to discuss study progress and any issues or concerns as they arise. Given this is a supportive care study, we do not anticipate any serious adverse events to be related to participating in the study. However, participating sites will contact the MGH team either via telephone or email to report any adverse events within 48 hours of their occurrence.

6.3 Data Storage to maintain confidentiality

All patient information will remain confidential and stored on Partners computers and in REDCap. Since these records necessarily contain patient identifiers, only study staff will have access to them. Identifiers such as name will only be used during the initial data retrieval process and can be destroyed once all data records have been obtained and data analysis completed. Data abstracted from the Electronic Health Record will be maintained in REDCap. REDCap is a free, secure, HIPAA-compliant web-based application hosted by the Partners HealthCare Research Computing, Enterprise Research Infrastructure & Services (ERIS) group. Vanderbilt University, with collaboration from a consortium of academic and non-profit institutional partners, has developed this software toolset and workflow methodology for electronic collection and management of research and clinical study data. Data collection projects rely on a study-specific data dictionary defined by members of the research team with planning assistance from Harvard Catalyst and The Harvard Clinical and Translational Science Center EDC Support Staff. The iterative development and testing process results in a well-planned data collection strategy for individual studies. REDCap provides flexible features that can be used for a variety of research projects and provides an intuitive interface to enter data with real time validation (automated data type and range checks). The system offers easy data manipulation with audit trails, reports for monitoring and querying participant records, and an automated export mechanism to common statistical packages (SPSS, SAS, Stata, R/S-Plus).

PROTOCOL TITLE: Multi-Site Randomized Trial of Inpatient Palliative Care for Patients with Hematologic Malignancies Undergoing Hematopoietic Stem Cell Transplantation

7.0 Study Timelines

Table 1 depicts the expected study timeline:

Time Point	Table 1: Study Procedure
Months 0-2	Finalize protocol development and submit to Institutional Review Board approval
Months 3-6	
Staff Training
 
 ❖ Hire RAs at each site and train them in study procedures, recruitment, and data collection. ❖ 2-day visit to Boston for Duke and Fred Hutchinson investigators and RAs to finalize study standard operating procedures. ❖ 1-day palliative care clinician training (in-person for co-investigators) and via video conference to review the palliative care intervention guide and on use of REDCap.
Months 7-43	
Randomized Controlled Trial:
 
 ❖ Enroll and randomly assign 360 patients (180 per study group) to receive either inpatient integrated palliative and transplant care vs. transplant care alone across three study sites. ❖ 2-day visit to Boston for Duke and Fred Hutchinson investigators and research assistants to review study progress and assess the fidelity of data collection and data entry (month 20).
Months 44-56	
Data Collection:
 
 ❖ Complete longitudinal data collection with a minimum of 1 year follow-up on all study participants. ❖ 2-day visit to Boston for Duke and Fred Hutchinson investigators and research assistants to review outcome measures and plan for dissemination of study findings (month 53).
Months 57-60	
Data Analysis:
 
 ❖ Complete data analysis and submit primary manuscripts. ❖ Prepare and submit grant proposal for large scale multi-site dissemination and implementation study.

Each subject will be enrolled for approximately one year to collect patient-reported outcomes. We estimate that we will complete the primary manuscripts in months 57-60 from the study start period.

8.0 Study Endpoints*

8.1 Primary endpoint:

- Compare patient QOL (FACT-BMT) scores at week 2 between the study groups

8.2 Secondary endpoints:

- Compare patients' QOL (FACT-BMT) longitudinally between the study groups
- Compare patients' symptoms (ESAS) scores between the study groups
- Compare patients' fatigue (FACT-fatigue) scores between the study groups
- Compare patients' depression and anxiety symptoms (HADS and PHQ9) between the study groups
- Compare patients' post-traumatic stress symptoms (PCL-C) between the study groups
- Compare caregivers' QOL (CARGOQOL) scores between the study groups
- Compare caregivers' anxiety and depression symptoms (caregiver HADS and PHQ9) between the study groups

8.3 Exploratory endpoints

- Compare patient coping (Brief Cope) between the study groups

PROTOCOL TITLE: Multi-Site Randomized Trial of Inpatient Palliative Care for Patients with Hematologic Malignancies Undergoing Hematopoietic Stem Cell Transplantation

- Compare caregiver coping (Brief Cope) between the study groups
- Assess whether group differences in patient-reported QOL (FACT-BMT) are mediated by improved symptom burden (mediator: ESAS/HADS), or coping (mediator: Brief Cope)
- Assess whether patient or transplant related characteristics are moderators of the impact of palliative care intervention on patient-reported QOL

9.0 Procedures Involved

9.1 Study design

We propose a multi-site randomized controlled trial of inpatient integrated palliative and transplant care versus transplant care alone in 360 patients with hematologic malignancies hospitalized for HCT and 180-360 of their caregivers. Patients will be randomized in 1:1 fashion and stratified by study site and transplant type (autologous vs. allogeneic). As autologous and allogeneic HCT have significantly different courses of recovery post-transplant,¹ we will stratify by the type of transplant to ensure adequate and balanced representation between the two study groups

9.2 Palliative Care Intervention:

Patients randomized to the palliative care intervention will meet with a palliative care clinician within 48 hours of randomization (excluding weekends). After the initial visit, the palliative care clinicians will meet with patients at least two times per week during their hospitalization. Patients, caregivers, or the palliative care clinician may initiate additional visits as needed.

Table 2: Palliative Care Intervention Domains		
Domain	Elements	Key Points
Therapeutic Relationship	
 • Introducing role palliative care • Understanding the patient and caregiver experience • Building trust with the patient and caregiver 	
 • Develop a strong therapeutic relationship with patients and caregivers • Learn about the values, life goals, and experiences of patients and their caregivers both prior to and after the cancer diagnosis • Develop trust and credibility with patients and caregivers by providing reassurance and outlining parameters of communication
Assessment and Treatment of Patient Symptoms	
 • Preparing for symptoms • Assessing & treating symptoms • Coordinating symptom management with HCT team • Providing referral for symptom management 	
 • Clarify the symptoms the patient will likely experience and offer reassurance about the methods for reporting and treating symptoms • At every visit, elicit existing and new symptom concerns with emphasis on common HCT symptoms (nausea, pain and mucositis, fatigue, sleep disturbances, constipation, diarrhea, anxiety and depression) • Maintain ongoing, effective communication with HCT clinicians to define mutual collaboration and work within their preferred practice patterns • Emphasize team approach to care by referring to specialty care, mental health, alternative medicine, and spiritual support as needed
Managing Patients and Caregivers Expectations	
 • Reviewing in-detail the expected illness trajectory during HCT • Ensuring accurate expectations throughout the HCT process • Enhancing patients' and caregivers' understanding and acceptance of the illness 	
 • Address early on patients and caregivers' concerns about the trajectory of illness during HCT and treatment side effects • Reassure patients and caregivers that QOL deterioration is expected, temporary and does not indicate worsening health status or unsuccessful HCT • Recognize that illness acceptance involves cognitive, emotional, and behavioral elements and offer a safe venue for patients and caregivers to ask questions about their disease and HCT process
Coping with Illness and HCT	
 • Reviewing & validating prior coping efforts • Discussing & advocating for different methods of coping 	
 • Recognize that patients and caregivers bring their own expertise in coping to the current circumstance based on prior experiences • Introduce strategies to help improve adjustment (e.g., behavioral, cognitive, and spiritual approaches; accepting illness while maintaining hope; social support)

PROTOCOL TITLE: Multi-Site Randomized Trial of Inpatient Palliative Care for Patients with Hematologic Malignancies Undergoing Hematopoietic Stem Cell Transplantation

	
 • Supporting caregiver coping • Providing referral for additional support 	
 • Bolster caregiver coping by assessing burden, enhancing their communication with patients, and recommending additional support • Involve other members of the team for patients and caregivers who may be experiencing severe distress (e.g., social work, psychology)
--	--	---

As shown in Table 2 above, the palliative care intervention will focus on the following content areas: 1) addressing patients' physical and psychological symptoms; 2) managing patients' and caregivers' expectations; and 3) providing patients and caregivers with strategies to cope with the illness during HCT. Palliative care clinicians will focus specifically on symptoms we have shown to be prevalent in this population, including nausea, pain and mucositis, fatigue, sleep disturbances, constipation, diarrhea, anxiety and depression.

Ensuring Fidelity of the Palliative Care Intervention: We will take several steps to ensure the fidelity of our study design, training, and intervention delivery as noted in the table below (Table 3). Specifically, for the study design, we will utilize an evidence-based palliative care intervention guide, measure the number and duration of palliative care visits, and monitor the number of participants in the control arm receiving palliative care. Also, we will employ rigorous training procedures with in-person training for site PIs and RAs; and monthly telephone conferences with Drs. [name] and [name] with the site PIs and palliative care clinicians to discuss any issues. To ensure the fidelity of the intervention delivery, we will review palliative care clinicians' documentation to enable us to assess the content of the clinical encounter. Drs. [name] and [name] will independently review electronic surveys completed by the palliative care clinicians to ensure intervention fidelity and conformity between sites in addressing the domains and topics as specified by the guide. Based on this review, Drs. [name], [name], and [name] will provide constructive feedback as needed to individual clinicians to ensure they are delivering the intervention in a consistent fashion. The site PIs will also review palliative care notes in the health record to ensure adherence to the intervention guide content and provide feedback to clinicians at the site research meetings.

Table 3: Fidelity	Steps Taken to Ensure Fidelity	Fidelity Assessment
Study Design	
 - Intervention based on a well-defined conceptual model and systematic review of literature - Standard intervention dose with clear feasibility data based on prior work - Cross-contamination not expected to be a major issue given lack of palliative care consults in HCT 	
 - Utilize evidence-based palliative care intervention guide based on prior trial - Measure number of intervention visits & visit duration using the palliative care clinician survey - Measure number of participants in standard-of-care receiving palliative care
Training	
 - Use if a palliative care intervention guide - Initial in-person training of site PIs on study protocol and palliative care intervention - Initial in-person training of site RAs on study procedures - Initial full-day training of all palliative care clinicians (all sites) with Drs. [name] and [name] using video conferencing - Monthly conference calls (led by Drs. [name] & [name]) with site PIs and palliative care clinicians to address study issues - Annual retraining seminar via video conferencing with all palliative care clinicians (at all sites) 	
 - Complete review of intervention guide - Complete training of all site-PIs in protocol administration and intervention delivery - Complete training of all site RAs on protocol and study procedures - Assess pre- and post-knowledge that palliative care clinicians acquired during training - Send meeting minutes from conference calls to all site PIs, palliative care clinicians, and research assistants - Assess pre- and post-knowledge that palliative care clinicians acquired during retraining
Intervention Delivery	
 - Utilization of palliative care intervention guide with standardized content areas - Completion of electronic survey after each encounter to record the content and topics that palliative care clinicians addressed during the visit and audio-record of all palliative care visits - Documentation of clinical encounter using standardized visit note template in site medical record 	
 - Conduct ongoing training of any new staff in standardized palliative care intervention guide - Drs. [name] & [name] will review palliative care electronic surveys monthly for 6 months and then every 4 months thereafter to ensure adherence to content, and [name] will review findings during monthly calls. - The site PI will review the first 3 notes for the first 15 participants on the PC arm, and then review 2 palliative care notes for each PC clinician every 6 months thereafter

9.3 Transplant Care Alone:

PROTOCOL TITLE: Multi-Site Randomized Trial of Inpatient Palliative Care for Patients with Hematologic Malignancies Undergoing Hematopoietic Stem Cell Transplantation

As done in our prior trial,³⁴ patients randomized to the transplant care alone arm will not meet with palliative care clinicians, though they may consult with palliative care at their request or at the discretion of their treating clinicians. In most transplant centers, supportive care measures are instituted at the discretion of the transplant oncology team and include symptom-directed therapies for nausea, pain, and diarrhea. Additionally, social workers are occasionally available to assist in helping patients and families emotionally during the HCT process. We will collect data on social work consultations and consider them as a covariate in our analyses. Patients randomized to transplant care alone will receive all supportive care measures as instituted by the transplant oncology team including social work consultations upon request. We anticipate minimal cross contamination, as the rate of palliative care consultation is less than 5% for patients admitted for HCT at our participating sites. In our prior single center trial, only two patients randomized to transplant care alone received palliative care consultations. Notably, the palliative care intervention did not lead to significant changes in supportive care practices implemented by the transplant clinicians. While patients undergoing HCT often interact post-transplant, they are typically isolated during the acute hospitalization period and have minimal interactions. Patients are also typically seen by multiple providers including nutritionists, physical therapists, residents, nurse practitioners, and social workers. Consequently, patients randomized to transplant care alone will not notice the lack of interaction with palliative care clinicians. Therefore, we do not anticipate that cross-contamination will be a significant issue in the proposed trial.

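### The protocol does not hold registration and randomisation until admission, so for patients randomised early the 48-hour first-visit rule conflicts with an inpatient intervention, and patients who never start inpatient HCT can enter the randomised set

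*Combined protocol and SAP*

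**What the plan says.** **Timing of enrolment.** Section 5.1 states that "the RA will approach patients for study participation two weeks prior to their admission date or within 72 hours of their admission for HCT", with a longer limit around public holidays. Verbal consent by telephone or video is allowed. Baseline may be completed at consent or "within the two-week window prior to their admission date or within the 72-hour window (excluding public holidays) from admission to the transplant unit". Sections 21.0 and 26.0 repeat the two-week route.

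**Registration.** Section 5.1: "Patients must sign informed consent or provide verbal consent and complete the baseline questionnaire before registering with the Clinical Trials Management System". Staff must also confirm the inclusion criteria on an eligibility checklist. Section 21.0 says that patients who have consented and completed baseline are then registered.

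**Randomisation.** Section 5.1: "Once the patient has been registered, a member from of the MGH Cancer Outcomes Research Program (CORE) team (independent from the study staff) will perform" the randomisation. Section 21.0 gives the same order.

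**Intervention.** Section 9.2 says that patients in the intervention arm "will meet with a palliative care clinician within 48 hours of randomization (excluding weekends"), then at least twice weekly in hospital. Section 11.0 (Participant Adherence) describes the intervention as taking place during the inpatient stay for HCT.

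**Eligibility.** Section 3.2 includes adults admitted for HCT. It excludes outpatient HCT and "Patients who already consulted Palliative Care during their HCT admission".

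**Primary assessment and analysis.** Section 9.7 places the week-2 assessment in hospital, from day +5 (autologous) or day +8 (allogeneic). Section 10.1 analyses completers first and also applies intention to treat to everyone randomised. Participants who withdraw or die "will not be replaced and they will count towards the accrual numbers".

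**The concern.** Read in order, these steps allow a patient to be consented, assessed, registered and randomised while still at home. The first-visit clock would then start before the patient is in the setting where the intervention is given. Three sites could resolve this in three ways: breach the visit rule, hold the first visit outside hospital, or delay randomisation without a written instruction.

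At stake are a visit rule that some patients cannot follow, an exclusion criterion that works for late enrollees but not early ones, and a randomised set open to patients who never have the inpatient transplant. Such patients have no in-hospital assessment at day +5 or +8, which is when the primary endpoint is measured, and the plan does not say how to analyse them.

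**Working it through.** **1. Is there a hold until admission?**

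| Section | Points to before admission | Points to after admission |
|---|---|---|
| 3.2 | – | Inclusion is worded as admitted for HCT |
| 5.1 | Approach, consent and baseline from two weeks before; randomisation follows registration | Inclusion criteria confirmed at registration |
| 18.1 | – | Approach on the inpatient unit, citing 5.1 |
| 21.0 | Same early route; patients then registered, then randomised | – |
| 26.0 | Two weeks before admission | Consent in a private hospital room |

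No section states that registration or randomisation waits for admission. Section 18.1 cites section 5.1 for an inpatient approach, while 5.1 also allows the earlier route. The sections conflict.

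**2. Can the first-visit rule be met?** Take a weekday randomisation and an admission 0 to 14 days later: 5 × 15 = 75 combinations. Count a combination as workable if no more than two weekdays pass before admission. This is generous, because it also accepts a weekend admission that follows the second weekday.

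- Monday or Tuesday: lead times of 0-2 days work, 2 × 3 = 6.
- Wednesday, Thursday or Friday: lead times of 0-4 days work, 3 × 5 = 15.
- Total workable: 21 of 75 (28%). Not workable: 54 of 75 (72%).

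This counts calendar combinations and does not forecast the share of patients. Patients randomised after admission, or very shortly before it, can comply.

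**3. Reproduce the stated power.** Inputs from section 10.2: 360 patients, difference 6.9, SD 20, two-sided 0.05, 10% missing. Allocation is 1:1 (section 9.1).

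- Evaluable per arm: 180 × 0.90 = 162.
- Standard error: 20 × √(2/162) = 2.222. Ratio: 6.9/2.222 = 3.105.
- Power: 87.4% by the normal approximation, 87.2% by the noncentral t. The stated 87% reproduces.

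**4. Effect of patients who never start inpatient HCT.** The documents give no rate. Assume that a share f of all randomised patients is affected, with f = 2.5% to 5%; that is 360 × 0.025 = 9 to 360 × 0.05 = 18 patients. Noncentral t throughout.

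| Case | f = 2.5% | f = 5% |
|---|---|---|
| Lost on top of the 10%: 162 × (1 − f) per arm | about 158 per arm, 86.4% | about 154 per arm, 85.5% |
| Kept with imputed zero effect: 6.9 × (1 − f), 162 per arm | 6.73 points, 85.5% | 6.56 points, 83.7% |

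The second row needs an imputation rule, because these patients have no in-hospital assessment. At an assumed f of 10%, that row falls just below 80% (79.6%; 79.8% by the normal approximation).

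**5. Could the allowance absorb it?** Section 10.2 reports 2% missing at week 2 in the prior trial. If that recurred (an assumption), total loss would be 2% + 2.5% = 4.5% to 2% + 5% = 7%. That leaves 171.9 to 167.4 per arm and power of 89.1% to 88.2%, above the stated 87%.

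**The case against.** The best defence is that early randomisation is inferred and never stated. The two-week window expressly covers only approach, consent and baseline. Staff must confirm the inclusion criteria at registration, and the first criterion speaks of patients admitted for HCT, so registration could be read as waiting for admission. This stands as a possible reading, and it is why the point concerns an unresolved conflict. It does not settle the matter: section 21.0 moves directly from consent and baseline to registration, and no hold is written.

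Section 9.2 also attaches the hospital setting to the visits after the first and does not expressly require an inpatient first visit. That is true, but an earlier first visit would then be at odds with section 11.0.

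A reader might infer more than the documents support:

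- *That the first-visit rule cannot be met in this trial.* It fails only for patients randomised well before admission.
- *That patients with a cancelled transplant count towards the 360 and are not replaced.* The rule in section 5.1 names only withdrawals and deaths. It is silent on cancelled or outpatient transplants.
- *That the primary comparison is biased.* Nothing in the documents makes cancellation depend on arm. Controls who learn their allocation early might ask for palliative care more often, but this is speculation: section 9.3 already permits such consults and reports a rate below 5%, and section 9.2 plans to count them.

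**Conclusion.** The concern holds in a limited form. The protocol permits randomisation before admission by the order of its steps, contains other text that points the other way, and does not reconcile the two. For patients randomised more than 48 hours (excluding weekends) before admission, the visit rule and the inpatient setting conflict, and the exclusion on prior consults cannot operate. Patients who never start inpatient HCT can enter the randomised set without the scheduled primary assessment and without a handling rule.

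The numerical effect is small. It rests wholly on the assumed 2.5-5%, may vanish within the 10% allowance, and stays above 80% power over that range. The main cost is a rule that sites may apply differently and an analysis population that is not fully defined. The sample-size calculation itself is sound.

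**What to change.** Keep consent and baseline in the two weeks before admission. State in sections 5.1 and 21.0 that registration and randomisation take place only after the patient is admitted for inpatient HCT and eligibility is confirmed, including the exclusion for a palliative care consult during that admission.

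Reconcile sections 3.2, 5.1, 9.2, 11.0 (Participant Adherence), 18.1, 21.0 and 26.0 on this timing and on what starts the first-visit clock. The choice of visit window is for the sponsor.

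Add a sentence to section 10.1 on how a randomised patient who does not start inpatient HCT is analysed. Later randomisation would make such cases fewer but would not cover a transplant cancelled after admission.

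The cost is protocol wording and a change in when the central team runs the randomisation. Allocation becomes known slightly later for patients who consent early, and randomisation must be run promptly at admission.
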